## REVISION HISTORY

Revision Number	Release Date	Change	Reason for Change	DCO #
A	03-Apr-2017	Initial release.	N/A	02749
B	26-Jul-2017	Primary change – Study Population is UUI	To address FDA response to Rev A	03006
C	31-Aug-2017	Primary changes – Revised UUI inclusion criteria, exclusion criteria, and treatment success criteria	To address FDA response to Rev B	03122
D	03-March-2018	Minor updates to clarify Sections on check-in call schedule, study diagram, study schedule, and lead issues	To ensure consistent information across protocol and SAP	03602
E	18-SEPT-2018	Added details of statistical analysis methods from the SAP to the protocol – specifically, primary and secondary endpoints analysis methods, study populations, analysis sets, handling of missing data, sensitivity analysis.  Updated language on restarting activation date after lead replacement.	To address FDA response to Rev D	04442
F	06-NOV - 2018	Changed the primary endpoint population to include all implanted subjects per FDA study design consideration  Added clarification on the alpha allocation for secondary endpoints	To address FDA study design recommendations and clarify alpha allocation for secondary endpoint analysis	04602
G	11-FEB-2019	Updated MEDDEV version	Used the appropriate MEDDEV version for CE mark approved devices	04940

## STUDY SYNOPSIS

Study Title:	Axonics Sacral Neuromodulation System for Urinary Urgency Incontinence Treatment: ARTISAN-SNM
Study Device:	Axonics Sacral Neuromodulation System (SNM) System
Study Design:	Single-arm, prospective, multi-center, unblinded pivotal study
Indication for Use:	Axonics Sacral Neuromodulation Therapy for Urinary Control is indicated for the treatment of the symptoms of Urinary Urgency Incontinence (UUI) in patients who have failed or could not tolerate more conservative treatments.
Primary Objective:	To evaluate the safety and effectiveness of the Axonics Sacral Neuromodulation System as an aid in the treatment of the symptoms of UUI designed to gain pre-market approval in the United States.
Secondary Objective:	To evaluate the technical performance and health economics of the Axonics SNM System and the quality of life of patients in the treatment of the symptoms of UUI.
Subjects:	Up to one hundred and forty-five (145) subjects enrolled or at least one hundred and sixteen (116) implanted subjects
Centers:	Up to 20 centers (U.S., Canada, and Western Europe)
Study Duration:	The study duration is expected to be approximately 36 months. The enrollment phase will be approximately 12 months. Subjects will participate in the study for 24 months post activation.
Primary Effectiveness Endpoint:	Proportion of all implanted subjects that are Treatment Responders (i.e. subjects with $\geq 50\%$ reduction in the number of urgency leaks) is greater than 50% at 6-months post activation.
Secondary Endpoints:	The following secondary endpoints are planned in all implanted subjects at 6-month follow-up 

• Improvement from baseline in ICIQ-OABqol total score (HRQL)

- Reduction from baseline in average daily number of urgency leaks
- Reduction from baseline in average daily number of large urgency leaks
- Reduction from baseline in average daily urgency
- Improvement from baseline in average daily number of voids

Additionally, the following endpoint is planned in Trial Responders cohort at 6-month follow-up:

- Responder rate

**Primary Safety Endpoint:** Rate of adverse events (AEs) at 6 months post-activation

**Safety Measures:** Adverse device effects (ADEs)

Adverse procedure effects (APEs)

Serious adverse events (SAEs)

Serious adverse device events (SADEs)

**Performance Measures:** Device performance metrics

Leaks per day with associated urgency and leak magnitude (72-hour voiding diary)

Quality of life questionnaires (EQ-5D, ICIQ-OABqol)

Subject satisfaction with treatment

Bowel function questionnaires (CCF-FIS, CCCS)

Medication usage

Healthcare utilization

**Inclusion Criteria:** Diagnosis of UUI demonstrated on a 72-hour voiding diary defined as:

- a minimum of four (4) leaking episodes associated with urgency,
- at least 50% of all leaking episodes associated with urgency, and
- at least one leaking episode each 24-hour period.

Greater than or equal to 6 months' history of UUI diagnosis

For male subjects only:

- Peak flow rate > 15 cc/s as verified by uroflowmetry within 6 months prior to enrollment
- Residual bladder volume < 150 cc tested within 6 months prior to enrollment

Positive motor response on at least two (2) implanted electrodes during intraoperative test in the S3 (preferred) or S4 foramen

21 years of age and older

For patients' over 70 years of age, or any patient at the discretion of the Investigator, Edmonton Frail Scale score of 9 or less

Failed conservative therapy and second-line drug therapy and is not a candidate for additional conservative or second-line therapy

No changes to current regimen of medications that affect bladder function for at least four (4) weeks prior to beginning the baseline voiding diary and baseline questionnaires

Willing and capable of providing informed consent

Capable of participating in all testing associated with this clinical investigation

**Exclusion Criteria:**

More than minimal level of stress incontinence or mixed incontinence with stress component likely to confound study outcome.

Current urinary tract mechanical obstruction (e.g. benign prostatic enlargement or urethral stricture)

Interstitial cystitis or bladder pain syndrome as defined by either AUA or EAU guidelines

Chronic pelvic pain

History of any pelvic cancer

Uncontrolled hypertension

Any significant medical condition that is likely to interfere with study procedures, device operation, or likely to confound evaluation of study endpoints (e.g. Crohn's disease, moderate to severe fibromyalgia, chronic pain, etc.)

Any psychiatric or personality disorder at the discretion of the study physician

PHQ-15 score of  $\geq 15$

Current symptomatic urinary tract infection (UTI) or more than three (3) UTIs in past year

Any neurological condition that could interfere with normal bladder function, including stroke, epilepsy, multiple sclerosis, Parkinson's disease, clinically significant peripheral neuropathy, or spinal cord injury (e.g., paraplegia)

Uncontrolled diabetes (A1C > 6.5, documented in the last three (3) months)

Diabetes with peripheral nerve involvement

Treatment of urinary symptoms with botulinum toxin therapy within twelve (12) months prior to SNM implant date

Treatment of urinary symptoms with tibial nerve stimulation within three (3) months prior to SNM implant date

Previously implanted with a sacral neuromodulation device

Underwent an external trial and was deemed a non-responder

Pelvic organ prolapse stage 3 or higher

History of pelvic floor surgery, including surgical treatment for stress incontinence or prolapse, within 6 months prior to SNM implant date

Surgical treatment for stress incontinence (sling, Burch or urethral injection) or pelvic organ prolapse recommended or planned at enrollment

History of allergic response to titanium, zirconia, polyurethane, epoxy, or silicone

Knowledge of planned MRIs on areas other than the head, diathermy, or high output ultrasonic exposure

Any other active implanted devices (e.g., drug delivery pumps, pacemaker, ICD) including neurostimulators whether turned on or off. Passive implants (e.g., prostheses) are allowed, but no implanted metal should be at the Neurostimulator implant site

A female who is breastfeeding

A female with a positive urine pregnancy test

Currently participating in another clinical trial

**Sample Size Justification:** The study sample size was initially determined considering that

the primary endpoint analysis will be performed in the Trial Responders cohort. The sample size considerations using these assumptions is provided in detail in previous versions of the protocol (Rev A- Rev E).

Based on FDA input, the primary endpoint analysis cohort was changed to all implanted subjects. At this stage (rev F), all subjects have been enrolled and implanted. A justification for why the currently implanted number of subjects is a sufficient sample size is provided below:

The primary effectiveness endpoint hypothesis is that the proportion of all implanted subjects that are Treatment Responders at 6-months is greater than 50% (null proportion).

1. Previous literature on SNM for UUI treatment was used to estimate the expected success rate of all subjects receiving this treatment. These studies have shown approximately 80-85% of the subjects that receive an external trial proceed to a permanent SNM implant. Long-term (>6 month) clinical success is seen in approximately 80-85% of the subjects with permanent implant. Thus, of all subjects that received SNM therapy, approximately 65-70% are therapy responders at long term follow-up.
2. Assuming that the true proportion of Treatment Responders is 65%, one hundred and sixteen (116) implanted subjects at 6-months provides approximately 90% power to show that the percentage of Treatment Responders is greater than 50%, assuming a one-sided Type I error rate of 0.021. The one-sided Type I error rate of 0.021 is used to account for planned early look analyses (per the Statistical analysis plan).
3. Assuming an attrition rate of 20% between enrollment and the implant procedure due to screen failures and withdrawals, the total number of enrolled subjects will be capped at approximately one hundred and forty-five (145). Therefore, the study will continue to enroll subjects until either:
  - One-hundred and forty-five (145) patients are enrolled

---


 White WM, Mobley JD 3rd, Doggweiler R, Dobmeyer-Dittrich C, Klein FA. Incidence and predictors of complications with sacral neuromodulation. *Urology*. 2009 Apr;73(4):731-5.

[figure not shown]
("Enrollment Cap"), or

- There are at least one hundred and sixteen (116) implanted subjects.

Our primary endpoint analysis will be conducted in **All implanted** subjects.

A secondary endpoint analysis will also be performed in the Trial Responder cohort to be comparable to the published literature and standard clinical practice whereby subjects are only implanted after a successful trial period with an external stimulator.

**Figure 1: Study Schematic**

\*3-week visit is not mandatory if patient is already a Trial Responder

\*\*Check-ins are calls or visits without data collection

**Table 1: Study Visit Schedule**

Visit	Baseline	Implant	Activation (Day 0)	1-Week Visit (Day 7 ± 4)	2-Week Visit (Day 14 ± 4)	3-Week Visit (Day 21 ± 7)*	1-Month Visit (Day 30 ± 7)	2-Month Visit (Day 60 ± 10)	3-Month Visit (Day 90 ± 10)	6-Month Visit (PEP) (Day 180 ± 20)	9-Month Visit (Day 270 ± 30)	1-Year Visit (Day 365 ± 30)	18-Month Visit (Day 545 ± 30)	2-Year Visit (Day 730 ± 45)	Unscheduled
Informed Consent	X														
Demographics & Medical History	X											X		X	
Inclusion/ Exclusion Criteria	X														
Vital Signs	X	X	X	X	X	X	X	X	X	X	X	X	X	X	X
PHQ-15	X														
Edmonton Frail Score	X														
Adverse Event Form	X	X	X	X	X	X	X	X	X	X	X	X	X	X	X
Procedure Report		X													
Device Performance			X	X	X	X	X	X	X	X	X	X	X	X	X
72-hour Voiding Diary	X			X	X	X	X	X	X	X	X	X	X	X	X***
EQ-5D	X										X		X		X
CCCS**	X						X		X	X	X	X	X	X	
CCF-FIS***	X						X		X	X	X	X	X	X	
ICIQ-OABqol	X						X		X	X	X	X	X	X	
Subject Satisfaction with Treatment					X		X		X	X	X	X	X	X	
Medication Usage & Healthcare Utilization	X				X		X		X	X	X	X	X	X	X

\*3-week visit is not mandatory if subject is responding positively to programming and does not need reprogramming.

\*\* CCCS survey will only be asked after Baseline for patients that had a qualifying score (15 or greater) at Baseline.

\*\*\*CCF-FIS survey will only be asked after Baseline for patients that had a qualifying score (6 or greater) at Baseline.

\*\*\*\*If unscheduled visit is planned in advance, subject should be asked to complete a diary prior to the visit.

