## 1.5 Effectiveness Endpoint

The primary effectiveness endpoint is defined as the percent of all implanted subjects who have 50% or greater reduction in the number of urgency leaks at six (6) months (*Details in Section 5.2.3.1*).

The following metrics will also be measured according to the study schedule in Table 1:

- Device performance metrics
- Leaks and voids per day with associated urgency and leak magnitude (72-hour voiding diary)
- Quality of life questionnaires (EQ-5D, ICIQ-OABqol)
- Subject satisfaction with treatment
- Bowel function questionnaires (CCF-FIS, CCCS)
- Medication usage
- Healthcare utilization

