## 1.6 Study Justification

The study will be a prospective, multi-center, single-arm pivotal study. Subject outcomes will be compared to their baseline, with subjects serving as their own control. This study will use a performance goal as the primary endpoint metric.

Based on the evaluation of pre-clinical data, risk analysis and that SNM is a well-established therapy, a single-arm study should be sufficient to evaluate the safety and effectiveness of the device. As noted in a recent review, numerous studies have been conducted on SNM therapy, including randomized, controlled studies, and this study is expected to provide clinical data comparable to published results.

The study is anticipated to begin enrollment in the second half of 2017 and is expected to complete enrollment within 12 months. The study will be conducted at a maximum of twenty (20) centers in the United States, Canada, and Western Europe. The scheduled visits are shown in the Study Schematic (Figure 1) and Visit Schedule (Table 1). Subjects will be permitted unscheduled follow-ups as needed.

Study sites and investigators will be selected according to the Axonics Site Selection Standard Operating Procedure. They will be selected based on their experience with SNM therapy and their ability to conduct clinical research. At least half of the study sites will be located in the United States to ensure that the outcomes are reflective of the U.S. patient experience.

Reports will be prepared when all subjects reach the primary endpoint, and after the all study subjects have completed their final study visit.

An independent Data Safety Monitoring Board will assess the safety of the device as the study progresses.

---

 Gormley, E. A., Lightner, D. J., Burgio, K. L., Chai, T. C., Clemens, J. Q., Culkin, D. J., Vasavada, S. P. (2014). Diagnosis and treatment of overactive bladder (non-neurogenic) in adults: AUA/SUFU guideline. Retrieved from <https://www.auanet.org/common/pdf/education/clinical-guidance/Adult-Urodynamics.pdf>.

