#### *4.2.7 CCF-FIS*

The Cleveland Clinic Florida Fecal Incontinence Score (CCF-FIS) is a five (5) question survey assessing severity of fecal incontinence symptoms. The questions cover incontinence to gas, liquid, solid, need to wear pad, and lifestyle changes. Each question is scored on a scale from zero (absent) to four (daily). The survey takes less than 5 minutes to complete.

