#### *4.2.8 CCCS*

The Cleveland Clinic Constipation Score (CCCS) is an eight (8) question survey that assesses the severity of constipation symptoms. The questions cover the frequency and difficulty of bowel movements, associated sensations of completeness and pain, and the subject assessment of time, assistance, and failure associated with their attempts to evacuate their bowels. The survey takes less than 5 minutes to complete.

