#### *5.2.4.2 Secondary effectiveness endpoints*

A total of six (6) secondary endpoints are planned, five (5) of which are in all implanted subjects, and one (1) in Trial Responder subjects. The analysis of all secondary effectiveness endpoints will be based on all available data. Details on handling of missing data are provided in Section 5.2.4.6.

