## 6 RISK/BENEFIT ANALYSIS

### 6.1 Risks

A risk assessment in accordance with ISO14971:2012 was conducted.

The risks of complications associated with implanting the Axonics SNM System are comparable with general risks associated with any standard surgical procedure. The following risks and discomforts have been identified in relation to the SNM therapy:

- Worsening of bladder and/or bowel function
- Allergic or immune system response to the implanted materials
- Change in sensation or magnitude of stimulation which has been described as uncomfortable by some subjects
- Infection
- Pain or irritation at Neurostimulator and/or Tined Lead site
- Seroma, hemorrhage, and/or hematoma
- Tined Lead or Neurostimulator migration or erosion
- Nerve injury (including numbness)
- Technical device malfunction
- Transient electric shock or tingling
- Unintended nerve activation
- Heating or burn at Neurostimulator site

The risks of the procedure include exposure to anesthesia and exposure to radiation from fluoroscopy. These risks are the same as expected from the procedure of the commercially available SNM system.

The risks associated with participation in this study will be similar to those associated with commercially available SNM therapies. The risks of participation in this study will be minimized by careful subject and site selection, as well as by implementing monitoring procedures to ensure proper conduct and management of the study.

Consult the device manuals for additional information regarding the risks associated with the Axonics SNM System. Any safety directive from Axonics to the ARTISAN-SNM investigators will be reported according to applicable regulations.

In case of any unexpected Adverse Device Effect or Serious Adverse Device Effect, investigators will be informed. Investigators shall forward this information to their IRBs/ECs as per local requirements. Any unexpected Adverse Device Effect or Serious Adverse Device Effect will be reported by Axonics in accordance with applicable US FDA regulations.

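### Bowel worsening is a named risk, but both bowel questionnaires are repeated only in subjects with high baseline scores: worsening elsewhere reaches the record only through unscored routes, and the re-measured subset is biased toward improvement

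*Combined protocol and SAP*

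**What the plan says.** Section 6.1 (Risks) includes "Worsening of bladder and/or bowel function" in its list of identified risks of the therapy.

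Table 1 marks CCF-FIS and CCCS at baseline for every subject and at seven later visits: 1, 3, 6, 9, 12, 18 and 24 months. Two footnotes then restrict all seven. For fecal incontinence: "CCF-FIS survey will only be asked after Baseline for patients that had a qualifying score (6 or greater) at Baseline". For constipation: "CCCS survey will only be asked after Baseline for patients that had a qualifying score (15 or greater) at Baseline". Each survey is gated on its own score.

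Section 1.5 and the synopsis list the bowel questionnaires as further or performance measures. Section 1.5 refers to Table 1 for timing and does not mention the restriction. They are not among the formal endpoints: Section 5.2.4.2 states "A total of six (6) secondary endpoints are planned, five (5) of which are in all implanted subjects", and none of the six is a bowel score.

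The design has no control arm. Section 1.6: "Subject outcomes will be compared to their baseline, with subjects serving as their own control".

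The text available gives no reason for the cut-offs, no analysis of the restricted scores, and no allowance for selection on baseline.

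**The concern.** A subject can develop new bowel dysfunction only if it was absent or mild at baseline. Those are the subjects in whom the questionnaires stop. The scored instrument is kept for the people who already have symptoms and withdrawn from the people in whom a new symptom would be a safety signal.

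Two consequences follow. First, the trial cannot state what proportion of implanted subjects had a worse bowel score after implant, although it holds a baseline score for all of them. Second, the scores that are collected come from subjects chosen for a high value on the same scale. With no control arm, some of any later fall is regression to the mean, and a reader could take it for a benefit of the device.

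At stake are the description of one named risk in a study meant to support pre-market approval, and the interpretation of an exploratory bowel summary.

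**Working it through.** The plan states no figure on this point, so there is none to reproduce. The check sets the capture routes side by side and then sizes the selection bias.

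**1. Routes open to a subject below the cut-offs**

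| Route | When | What it gives |
|---|---|---|
| CCF-FIS, CCCS | Baseline only | A score, with nothing to compare it with |
| Adverse event form (Table 1; Sections 8.6.1, 8.11) | Every visit, all subjects | Unscored; depends on subject report and investigator confirmation; no bowel prompt described |
| Medical history (Table 1; Section 4.2.1) | Baseline, 1 year, 2 years | Secondary diagnoses; names fecal incontinence but not constipation; no severity |

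A condition recorded at baseline counts as an adverse event only if its severity or frequency rises. For a subject with mild baseline symptoms, that judgment needs a comparison with baseline, and the repeat score is what the footnotes remove. Medical history recurs only after the 6-month primary safety endpoint, so up to 6 months adverse event reporting carries this risk almost alone.

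**2. Room to worsen on CCF-FIS**

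Section 4.2.7 gives five items scored 0 to 4, so the maximum is 5 × 4 = 20. A subject at 5 can worsen by 20 − 5 = 15 points without being re-scored. A subject at 6 is re-scored and can worsen by 20 − 6 = 14.

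**3. Regression to the mean in the re-measured subset**

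With no true change and normal scores, the expected fall is

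(1 − ρ) × SD × φ(k) / (1 − Φ(k)), with k = (cut-off − mean) / SD,

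where ρ is the test-retest correlation. The documents give no baseline mean, SD or ρ for either survey, so all three are assumptions.

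Example, CCF-FIS with mean 4 and SD 4: k = (6 − 4)/4 = 0.5; φ/(1 − Φ) = 0.352/0.309 = 1.14; 4 × 1.14 = 4.56, so the selected mean is 8.56. The fall is 0.1 × 4.56 = 0.46 at ρ = 0.9 and 0.4 × 4.56 = 1.83 at ρ = 0.6.

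| Survey, cut-off | Assumed mean, SD | Re-measured, of 116 | Fall, ρ 0.9 to 0.6 |
|---|---|---|---|
| CCF-FIS, 6 | 2, 3 | 9% (11) | 0.54 to 2.16 |
| | 3, 4 | 23% (26) | 0.53 to 2.13 |
| | 4, 4 | 31% (36) | 0.46 to 1.83 |
| | 5, 5 | 42% (49) | 0.46 to 1.86 |
| CCCS, 15 | 4, 4 | 0.3% (0) | 1.22 to 4.88 |
| | 6, 5 | 4% (4) | 1.10 to 4.39 |
| | 8, 5 | 8% (9) | 0.93 to 3.71 |
| | 10, 6 | 20% (23) | 0.84 to 3.34 |

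**4. Simulation with rounded, bounded scores**

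Normal scores put some subjects below zero (about 16% when mean equals SD), so four cases per survey set were checked with whole-number scores held within range: two mean/SD pairs for each survey, at ρ = 0.6 and 0.8. The CCCS maximum is not in the documents; 30 was assumed. With no true change, the re-measured subset fell by 0.87 to 1.96 on CCF-FIS and 1.79 to 4.25 on CCCS.

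Then 10% of subjects, chosen at random, were made to worsen by 5 points:

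| | CCF-FIS | CCCS |
|---|---|---|
| Mean change, all subjects | about +0.45 to +0.46 (worse) | about +0.47 to +0.50 (worse) |
| Mean change, re-measured subset | −0.4 to −1.5 (apparent improvement) | −1.3 to −3.7 (apparent improvement) |
| Worsened subjects never re-asked | 54% to 73% | 90% to 96% |

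**The case against.** The strongest reply is that bowel harm is not invisible. The adverse event form is completed at every visit for everyone. Its definition covers new occurrences and worsening of baseline disease, the DSMB adjudicates events, and medical history is taken again at 1 and 2 years. Medication and healthcare-use questions, also unrestricted, could leave an indirect trace. All of this stands. A reader might infer that worsening below the cut-offs goes wholly unrecorded, and the documents do not support that. A subject who goes from a score of 5 to severe incontinence is the case adverse event reporting is most likely to catch; the plausible gap is mild or gradual change.

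A reader might also infer that the bowel data can show benefit but not harm. That goes too far: re-measured subjects can still worsen, by up to 14 points from a CCF-FIS of 6. The bias concerns the subset's mean change and does not stop individual worsening from being seen. Nor does a place at the head of the Section 6.1 list imply a ranking of risks.

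It can further be said that these surveys are performance measures, that the indication is urinary only, and that no bowel-benefit hypothesis is planned. That is right, and it limits the consequence: regression to the mean matters only if the subset's mean change is presented as an effect. The sizes also rest on assumed distributions. Only the direction is secure.

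Finally, the change comes late. All subjects had been implanted by Rev F, so completed visits are lost.

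**Conclusion.** The point holds as a limit on measurement. Below the cut-offs there is no repeat bowel score, and worsening is captured only through unscored records, which for constipation do not include a named history item. The trial cannot report the proportion of implanted subjects whose bowel score worsened.

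The mean change in the re-measured subset is biased toward improvement whenever test-retest correlation is below 1. Its size cannot be determined from the documents. Illustratively it is about 0.5 to 2 points on CCF-FIS, and about 0.8 to 4.9 on CCCS with very few subjects re-measured in most cases. These figures assume a baseline mean of 2 to 5 (CCF-FIS) or 4 to 10 (CCCS), an SD of 3 to 5 or 4 to 6, and a correlation of 0.6 to 0.9.

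This is a cheap improvement to the safety description. The primary and secondary effectiveness conclusions do not depend on it.

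**What to change.** - Remove both Table 1 footnote restrictions for the remaining visits, so that all implanted subjects complete CCF-FIS and CCCS (for example at 6 months where not yet done, 1 year and 2 years).
- In the safety report, tabulate by visit the proportion whose score worsened from baseline and the proportion newly crossing 6 (CCF-FIS) or 15 (CCCS). State the denominator at each visit, because earlier visits cannot be recovered.
- Keep the baseline-qualifying subset as a separate exploratory summary. Do not present its mean change as a device effect without noting regression to the mean.
- Where visits have already passed, state the restriction in the report.

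The cost is two surveys of under five minutes each at visits that already take place, one added table, a protocol amendment, and uneven follow-up across visits. Baseline scores are already collected for everyone. If enrollment began no earlier than the planned second half of 2017, the earliest 2-year window opens about mid-May 2019 (1 July 2017 + 730 − 45 days). That is after the Rev G date of 11 February 2019, so at least that visit could be complete for all subjects still in follow-up.
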